**Resource Optimization in the Intensive Care Unit Setting: A Staff
Education and Scheduling Pilot Study to Improve Treatment
Decisions and Staff Satisfaction**

Study Protocol

Study ID: 20200060-01
Version Date: 05/29/2020

Project Title: Resource Optimization in the Intensive Care Unit Setting: A Staff Education and Scheduling Pilot Study to Improve Treatment Decisions and Staff Satisfaction

Principal Investigator: [name]

Co-Investigators [name], [name], [name], [name], [name], [name]

PART 1: INTRODUCTION

Intervention Description

This intervention pilot study has been developed for Intensive Care Unit (ICU) physicians and nurses by the Resource Optimization Network (RON) for implementation in The Ottawa Hospital (TOH) Civic Campus and the Montfort Hospital. The intervention targets ICU staff and is designed to reduce overall costs associated with ICU health care service delivery and improve staff satisfaction through reducing stress and associated burnout without sacrificing quality of care and patient outcomes. The intervention involves two components that (a) build ICU staffs' (i.e. physicians and nurses) knowledge to facilitate cost-effective and evidence-based decision-making about patient care (including tests, treatments, and procedures); and (b) optimize nurse scheduling to ensure the presence of the appropriate number of nurses per shift, thereby reducing stress, burnout and limiting the need for overtime. To evaluate the impact of the intervention, a pre/post-intervention design will be employed, with a 3-month pre-intervention period, followed by a 6-month intervention period and a 3-month post-intervention period.

Rationale for the Intervention

It is estimated that care provided in the ICU in Ontario is approximately three times more costly compared to hospitalization in a regular ward, as patients in the ICU present complex and severe clinical issues that require intensive monitoring and the use of multiple health care resources. For instance, in Ontario, the average daily cost in the ICU at a teaching hospital is valued at \$4,186, while an acute care bed costs \$1,492 per day (1). With increasing life expectancies and an aging population in Canada, resource consumption in the ICU is expected to rise due to issues such as increasing complexity of conditions, need for increased surveillance and monitoring, and prolonged duration of stay in the ICU (2). According to data estimates by the Canadian Institute of Health Information (CIHI), it is predicted that by 2026, ICU usage may increase up to 80% (3).

Recently at TOH, expenditures have exceeded the annual budget and subsequent staffing changes have resulted in fewer positions for allied health professionals (e.g. physiotherapists, social workers) who often contribute significantly to improved and more efficient care of patients

in the ICU. Due to the elimination of such positions, ICU physicians and nurses are expected to take on more responsibilities in the ICU settings. These changes however may have contributed to the recently reported increased rates of absenteeism as well as burnout among ICU clinicians (4). This also has implications for patient care and hospital costs with several studies revealing clinical impacts of burnout to include decreased well-being, increased sick leave and lower self-rated performance among ICU staff (5,6). Furthermore, in 2016, it was estimated that the costs associated with nurse absenteeism and overtime totalled over \$536 million⁷in Ontario (7).

Our research group (the RON) has studied a number of ICU interventions that have shown positive outcomes in terms of reducing costs while maintaining or even improving care. These include initiatives such as early palliative care involvement, early tracheostomy, and intensivists staffed NACU that once implemented, resulted in reduced ICU spending (8–10). In addition, Choosing Wisely Canada has launched a campaign to increase awareness around the appropriate use of clinical and treatment resources in critical care units by engaging and supporting health care professionals to take leadership in identifying and reducing unnecessary tests, treatments and procedures that are not supported by evidence and could harm patients (11). In terms of reducing burnout among staff, a systematic review investigating job satisfaction among critical care nurses found that shift worked and staffing were significantly correlated to critical care nurses' job satisfaction (12). Therefore, initiatives to optimize scheduling that effectively address staff burnout resulting from too much work with inadequate recovery are needed. We propose that the adoption of such programs in the ICU may result in savings of approximately one million dollars per year for both TOH and the Montfort Hospital.

The specific objectives of this intervention study are to:

1. Reduce ICU costs by reducing unnecessary ICU tests, treatments, and procedures and reducing the use of overtime
2. Improve staff satisfaction through reducing staff stress and burnout by optimizing staff scheduling

PART 2: DESCRIPTION OF INTERVENTION

Intervention Population

The intervention will target ICU staff, with one component geared generally for ICU staff (i.e. physicians and nurses) and one component geared specifically for ICU nurses.

Staff inclusion criteria: Employees who are a) aged 18 years or older; and b) providing direct patient care in the ICU at the Civic Campus of the Ottawa Hospital or the Montfort Hospital as a physician or nurse.

Recruitment

In order to recruit ICU staff for participation in the educational workshops, a recruitment email invitation will be sent to all eligible ICU staff (i.e. physicians and nurses) and posters will be posted in staff breakrooms and high traffic zones (i.e. washrooms, ICU hallways). These recruitment invitations will explain to staff that participation in all intervention activities is voluntary and light refreshments will be provided. The email will also inform staff that the workshop will be held during a routine departmental meeting thereby maximizing convenience to promote participation.

Setting

This is a multicenter study. Study sites include the ICUs at two teaching hospitals in Ottawa: The Ottawa Hospital, Civic Campus and the Montfort Hospital.

Intervention Components

During an initial project meeting, the RON, a multidisciplinary team that includes experts in clinical ICU, analytics and scheduling, health economics and human factor engineering collaborating across various disciplines (nursing, pharmacy, physiotherapy, administration and management) evaluated the current status of the ICU service delivery, clinical outcomes and associated costs. Based on this, the team identified areas that could be easily modified while having a significant impact and designed relevant interventions to address areas best-suited to the ICUs at The Ottawa Hospital - Civic Campus and the Montfort Hospital (i.e., factoring in the culture of the ICU in their decisions).

There are two specific components that will be implemented concurrently over the 6-month intervention period, one targeted for ICU staff (i.e. physicians and nurses) and one targeted specifically for ICU nurses.

Component 1 – Educational Workshop: An educational workshop to increase ICU staffs' (i.e. physicians and nurses) awareness of the current Choosing Wisely Canada Critical Care strategies and recommendations to facilitate cost-effective and evidence-based decision-making about patient care (including tests, treatments, and procedures).

Component 2 - Optimizing Staff Scheduling: A strategy to optimize staff scheduling for ICU nurse (e.g. “staffing up” approach where more staff will be scheduled) in order to reduce overtime, absenteeism, stress and burnout of ICU nurses.

We propose that the adoption of such programs in the ICU may result in savings of approximately one million dollars per year for both TOH and the Montfort Hospital. The two intervention components will be implemented with ICU staff members over the 6-month intervention period.

PART 3: EVALUATION PLAN

Goals of Evaluation

To evaluate the impact of this multicenter intervention, a pre/post-intervention design will be employed, with a 3-month pre-intervention period followed by a 6-month intervention period and a 3-month post-intervention evaluation period.

The evaluation will assess the extent to which the intervention achieves its' objectives. The results of the evaluation will help determine: (1) intervention effectiveness in reducing overall costs associated with ICU health care service delivery and reducing staff stress and burnout and (2) intervention feasibility.

We will evaluate the following study outcomes:

1. Primary outcomes: The primary outcomes of focus are ICU costs and ICU quality metrics.
2. Secondary outcomes: The secondary outcomes of focus are patient outcomes, ICU medical procedures, staff absenteeism, staff stress levels and burnout, and stakeholder perceptions.

Methods

Respondents

The evaluation will involve collecting data from intervention participants, namely ICU staff at the Ottawa Hospital Civic Campus and at the Montfort Hospital.

Staff inclusion criteria: Employees who are a) aged 18 years or older; and b) providing direct patient care in the ICU at the Civic Campus of the Ottawa Hospital or the Montfort Hospital as physicians, nurses, or allied health professionals (e.g., respiratory therapists, occupational therapists).

Stakeholder staff inclusion criteria: Employees who are a) aged 18 years or older; and b) whose roles provide them with direct knowledge of the ICU at the Civic Campus of the Ottawa Hospital or the Montfort Hospital and the interventions implemented during the study period (e.g., nurse managers, ICU managers, medical site lead).

Hospital administrative data, including patient data from all patients who are a) aged 18 years of older; and b) admitted to the ICU at the Civic Campus of the Ottawa Hospital or the Montfort Hospital during the 6-month study period will be collected to assess intervention effectiveness.

Sample Size

Patient Data: Based on historical data from TOH, we conservatively estimate there will be 120 potentially eligible patients admitted to the ICU at the Civic Campus per month. We therefore anticipate that data will be collected from approximately 360 patients in the 3-month pre-intervention and 3-month post-intervention phases, respectively, and 720 patients during the 6-month intervention phase, equating to a total sample size of 1440 patients accrued over 12 months. At Montfort we estimate that the total sample size will be 500 patients over 12 months.

Of note, the data collected during the intervention period will not be included in the pre-post-intervention analyses. However, it will be used for quality assurance (i.e., stopping rules during interim analysis) and to further contextualize changes using run charts, as needed (e.g., of albumin use).

ICU Staff: Currently, there are approximately 194 staff members (i.e., intensivists, fellows, nurses, allied health professionals) providing direct patient care in the ICU at the Civic Campus and 50 staff members at Montfort. Based on previous research on survey and questionnaire response rates (13), we anticipate that at each time point (i.e., pre and post-intervention), 30% of ICU staff will complete the questionnaire, for a total sample size of approximately 58 respondents at TOH and 15 respondents at Montfort per time point.

ICU Stakeholder: We will aim to recruit between 5 to 10 relevant ICU stakeholder staff members at TOH and 3-5 staff members at Montfort (i.e., nurse managers, ICU managers, medical site

lead) for the post-intervention interviews. This sample size will ensure sufficient representation of stakeholder experiences, while bearing in mind the feasibility and time-involvement of qualitative data collection. These stakeholders will be purposefully sampled in order to ensure they are sufficiently information-rich (i.e., have knowledge of the ICU and the interventions that were implemented during the study) (14).

Recruitment

Recruitment for the online survey will take place via email, whereby all eligible ICU staff (i.e. physicians and nurses) will be sent an email containing a recruitment invitation and link to an online questionnaire during the pre-intervention and post-intervention periods. They will be informed that their participation is voluntary, and that informed consent will be obtained prior to gaining access to the survey. Specifically, the link will take participants to a consent form online, where they must agree to participate in order to access the questionnaire. To maximize recruitment, incentives will be offered for both the pre and post-intervention surveys. Specifically, at both time-points (pre/post intervention), staff who complete the questionnaire will be entered into a lottery draw for 2 Amazon gift cards valued at \$250 each.

During the post-intervention period, relevant stakeholders will be identified by the study team and purposefully selected to participate in the semi-structured interviews. A study invitation will be emailed to these stakeholders directly. It will be made clear in the invitation that their participation is completely voluntary, and that informed consent will be sought at the time of the interview.

Data Collection

i. Tools

A mixed-methods approach to collect data will be utilized. Quantitative data will be collected at 3-timepoints: 3-month pre-intervention, 6-month intervention period and 3-month post-intervention. Qualitative data collection will be collected at intervention conclusion. Data collection techniques include: (1) hospital administrative data, including patient data collected from TOH Data Warehouse and Montfort's Department of Archives and Decision Support (2) a questionnaire comprised of validated instruments for ICU staff, (3) a post- educational workshop evaluation survey, and (4) key stakeholder interviews with ICU staff post-intervention.

Quantitative Data

1. TOH Data Warehouse and Montfort's Archives: We will use data collected from TOH Data Warehouse and Montfort Archives to measure costs, patient quality metrics, ICU medical procedures and staff absenteeism during the study period.

ICU costs: Case costing will be used to determine the costs associated with ICU care during the study period, including: a) ICU total costs; b) ICU direct costs (i.e., all expenses to the hospital with fee codes linked to patient chart); c) ICU indirect costs (i.e., any overhead operational fees associated with service provided to patient); d) ICU cost/patient.

ICU Quality Metrics: The following outcomes will be included to evaluate the quality of ICU patient care during the study period: a) ventilator associated pneumonia; b) central line infections; c) C. difficile; d) number of patients receiving early mobilization

Patient outcomes: include a) length of stay (LOS); b) in-hospital mortality; c) patient and family satisfaction.

ICU medical procedures: Outcomes related to ICU medical procedures targeted in the educational intervention component will also be evaluated during the study period, including: a) albumin use; b) mechanical ventilation; c) chest radiographs; d) transfusion of red blood cells.

Staff absenteeism: We will collect data on ICU full-time staff absenteeism during the study period from the Data Warehouse and Montfort Archives.

2. Questionnaire: We will use an online questionnaire to evaluate ICU staffs' levels of stress and burnout. A self-administered online questionnaire taking approximately 15-20 minutes to complete will be used to obtain/assess pertinent demographic variables information (i.e., age, sex, ICU role [physician, resident, fellow; nursing; allied health]). Two instruments will be used to measure ICU staffs' level of perceived stress and job burnout.

The Perceived Stress Scale (PSS) (Appendix 1) (15) consists of 10 questions and is the most widely used psychological instrument for measuring perceptions of stress. The scale includes a number of direct questions to assess current levels of stress experienced and was designed to be non-content specific to any subpopulation.

The Maslach Burnout Inventory (MBI) (Appendix 1) (16) consists of 22 questions composed of three dimension that make up the construct of burnout: emotional exhaustion, depersonalization, and personal accomplishment. The MBI is the most widely used tool to measure burnout among professionals in the human services and has been validated in studies involving ICU nurses and physicians (5,6,17).

3. Post-educational workshop survey: A short survey will be handed out to participants in-person at the end of the educational workshop and emailed the day after. A sign-up sheet will be circulated at the beginning of the workshop to collect participants information including name, title and email address. Participant information collected will solely be for the purpose of sending the post-educational workshop evaluation survey. Participation in the workshop in no way obligates participants to respond to the survey. The survey will be voluntary and has been indicated as such in the Educational workshop consent form.

Qualitative Data

1. Semi-structured interviews with Stakeholders (staff): Post-intervention semi-structured interviews will be conducted with staff stakeholders by trained research staff and will use an interview guide to assess the stakeholders' perceptions of the intervention outcomes. Stakeholders will be asked about their knowledge of the interventions implemented during the study period, their perceptions of the outcomes of these interventions, and any perceived changes in ICU care delivery in time period that corresponds to the post-intervention phase of the study. The interview will last approximately 30 minutes and will be digitally-recorded and transcribed.

ii. Ethical practices and confidentiality of data

Steps will be taken to ensure that ethical standards for research involving human participants are followed.

The MRN of included patients will be required in order to link to OHIP numbers. Research staff will not see the OHIP numbers as they are added by the Performance Measurement designate as part of the transfer process.

For both quantitative and qualitative data collection, written consent informing respondents of interview procedure, risks and benefits, and measures of confidentiality will be obtained at the time of the interview or survey dissemination (18). Respondents will be briefed on the research purpose, and request to audio-tape for transcription (for interviews) and reminded of the voluntary nature of participation. Respondents will be reminded of the voluntary nature to share experiences, their right to refuse to answer or skip a question and withdraw at any point during or after the interview. Lastly, the form will offer the principal researchers' name and contact information. Consenting will be conducted in accordance with N2 SOP-008-06 – Informed Consent Process. At the start of the interview, the research staff member conducting the interview will introduce themselves, confirm the identity of the staff member, and review the study details with the participant in a quiet, private location of their choosing (when possible). The participant will be fully informed of all pertinent aspects of the research in non-technical language. The participant will be provided with a copy of the informed consent form and given time to read the form and ask questions. The research staff member will confirm understanding by asking questions about the material. Finally, two copies of the informed consent form will be signed by both parties, with a copy given to the participant and the other retained by the research staff member.

Confidentiality measures included: a unique identification number assigned to participants to ensure full de-identification in reports, transcriptions, analysis and audio files. The electronic list linking participant names with their study ID and the digital audio-recordings of the interviews will be encrypted and only authorized research team members will have access to the files. Audio files will be stored on an encrypted external drive and deleted at the end of the intervention. Identifiable variables, such as name, occupation, and ethnicity, will be removed from transcripts. Consent forms will be stored separately by the principal researcher in a locked filing cabinet. Data files will only be accessible to research personnel.

The staff satisfaction questionnaire will be anonymous and no identifying information will be collected from participants. This multicenter study will be coordinated by the Principal Investigator. Data will not be transferred between institutions and no TOH PHI or PII will be shared externally with the Montfort Hospital.

Sign-up sheets circulated at the beginning of the Education workshop to collect participants information including name, title and email address will solely be for the purpose of sending the post-educational workshop survey. Sign-up sheets will be destroyed immediately after sending the follow-up emails.

iii. Data Analysis

Pre-post intervention analyses will be conducted to evaluate the outcomes of the intervention. Specifically, t-tests will be used to test for differences in continuous outcome measures, while

differences between categorical variables will be assessed using χ^2 tests. Chi squared tests and t-tests will also be used to compare patient characteristics in the pre and post intervention periods to examine potential covariates (e.g., patient demographics, comorbidity scores). Based on these sensitivity analyses, multivariate regression models will be run to adjust for covariates in the study outcomes. A p-value < .05 will be considered statistically significant.

Interim analysis will be performed 3-months after the intervention period begins. The results of this analysis will be presented to a Data Safety Monitoring Board.

Post-intervention interviews with ICU staff members will be digitally recorded and then transcribed verbatim. A thematic analysis will be performed wherein the qualitative data will be coded and categorized into larger themes describing stakeholders' satisfaction and perceptions of the intervention outcomes (19).

REFERENCES

1. Care in Canadian ICUs [Internet]. Canadian Institute for Health Information; 2016 Aug. Available from: https://secure.cihi.ca/free_products/ICU_Report_EN.pdf

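### Staff satisfaction is the end point of Objective 2, but no staff-satisfaction measure is described before and after the intervention, so the study can test stress and burnout but cannot directly show whether satisfaction changed

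*Combined protocol and SAP*

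**What the plan says.** Satisfaction appears at three levels of the plan's aims. The title, part of which reads "Education and Scheduling Pilot Study to Improve Treatment", goes on to name staff satisfaction. The Intervention Description in Part 1 says the intervention is meant to "improve staff satisfaction through reducing stress and associated burnout without sacrificing quality of care and patient outcomes". The second specific objective is "Improve staff satisfaction through reducing staff stress and burnout by optimizing staff scheduling".

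Part 3, Goals of Evaluation, ties the evaluation to those aims: "The evaluation will assess the extent to which the intervention achieves its' objectives". The same section then states the effectiveness question in terms of costs, stress and burnout, and gives the secondary outcomes as "patient outcomes, ICU medical procedures, staff absenteeism, staff stress levels and burnout, and stakeholder perceptions".

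Under Data Collection, Tools, the online questionnaire is described as demographic items plus two scales: "Two instruments will be used to measure ICU staffs' level of perceived stress and job burnout". These are the PSS, with 10 questions, and the MBI, with 22 questions in three burnout dimensions. The section on ethical practices and confidentiality gives it a different name: "The staff satisfaction questionnaire will be anonymous and no identifying information will be collected from participants".

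The Data Analysis section expects the post-intervention interviews to produce themes that include stakeholders' satisfaction.

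**The concern.** Objective 2 sets out a chain: scheduling lowers stress and burnout, and that raises satisfaction. The plan measures the middle of the chain before and after the intervention, and collects absenteeism as well. It describes no measure of the last link, which is the one the objective names as its goal.

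Two things follow. If stress and burnout fall, whether satisfaction rose remains an assumption. If stress and burnout do not move but staff prefer the new schedule, the pre/post comparison has no variable in which that could appear. The gap is also time-critical, because a baseline that was not collected cannot be recovered once the pre-intervention survey has closed.

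**Working it through.** This is mainly a question of matching aims to measures, so each planned data source is set against what Objective 2 needs: staff satisfaction, in ICU staff, before and after.

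| Source (Part 3) | Who | When | Staff satisfaction? |
|---|---|---|---|
| Online questionnaire | ICU staff | Pre and post | None described; demographics, PSS and MBI only |
| Absenteeism data | Full-time ICU staff | Study period | No; at most an indirect marker |
| Patient outcomes | Patients and families | Study period | Satisfaction is listed, but not that of staff |
| Post-workshop survey | Workshop participants | End of workshop and next-day email | Content not described; no pre-intervention wave |
| Stakeholder interviews | Purposively chosen stakeholders | Post only | Themes possible; no baseline |

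No row gives staff satisfaction at both time points. The only source with the right people at both times is the questionnaire, and its described content is stress and burnout.

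**Numbers, from Sample Size and Tools**

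- Expected questionnaire respondents at 30% response: 0.30 × 194 = 58.2, stated as 58; 0.30 × 50 = 15.0, stated as 15. The plan's figures reproduce. Total per wave: 58 + 15 = 73.
- Interviewees: 5 + 3 = 8 at the low end and 10 + 5 = 15 at the high end.
- Scale questions: 10 + 22 = 32, all presented as measuring stress or burnout.

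**What an added measure could show.** The plan gives no power figure for staff outcomes. The following are assumptions: two-sided test at 0.05 (the plan does not state sidedness), 80% power, and two independent waves, because an anonymous survey without identifiers cannot be paired. The detectable difference in standard deviation units is then (1.960 + 0.842) × √(2/n), with n respondents per wave:

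- both sites, n = 73: 2.802 × √(2/73) = 0.46
- Ottawa Hospital alone, n = 58: 2.802 × √(2/58) = 0.52
- Montfort alone, n = 15: 2.802 × √(2/15) = 1.02 (the normal approximation is somewhat optimistic at this size)

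An added item would thus allow a moderate change to be detected with the sites pooled, and only a very large one at Montfort alone.

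**The case against.** The best defence is that the evaluation goals narrow the question. Goals of Evaluation says the study will determine effectiveness in reducing stress and burnout, and the secondary outcomes and instruments match that. The rationale also introduces a review of job satisfaction among critical care nurses under the heading of reducing burnout, so the authors treat the two as closely linked. This stands in part: most of the stated pathway is measured before and after. It does not close the gap, because the same section promises to assess the objectives, and nowhere does the plan say that stress and burnout scores are its definition of satisfaction.

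A reader might infer four stronger things that the documents do not support:

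- *Objective 2 cannot be answered at all.* Too strong. Its stress and burnout part can be tested; only the satisfaction part is without a measure.
- *The plan will report a fall in PSS or MBI scores as improved satisfaction.* Nothing in the analysis text says so. The loose label sits in a confidentiality paragraph, and the title states an aim, not a result.
- *The interviews exclude bedside staff.* Sample Size does list managers and site leads, but the eligibility rule offers such roles only as examples, and Tools and Data Analysis speak of interviews with ICU staff. The firm limits are the missing baseline, the small number and the purposive selection.
- *Staff are certainly never asked about satisfaction.* Appendix 1 is not in the text available for this review, and the content of the workshop survey is not described. The body cites Appendix 1 only for the PSS and MBI and speaks of two instruments, so the absence is a sound reading but not an item-level check.

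It is also fair that staff outcomes are secondary in a study that calls itself a pilot. That limits the importance of the point but does not remove it, since the plan still uses significance tests to judge effectiveness.

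**Conclusion.** The point holds in limited form. Satisfaction is the stated end of one of the two specific objectives, and the evaluation is meant to assess the objectives, but the plan lists no staff-satisfaction outcome and describes no satisfaction measure at either survey wave. Changes in stress and burnout can be tested; a change in satisfaction cannot be shown directly. Post-only interviews with 8 to 15 people cannot substitute for a before-and-after measure in about 73 respondents per wave.

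This rests on the questionnaire containing what the body text describes, and on the plan's own 30% response rate and staff counts. The conclusion does not depend on the exact number of respondents. The primary outcomes, ICU costs and quality metrics, are not touched. This should be corrected, but it does not threaten the study as a whole.

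**What to change.** Add a brief job-satisfaction measure to the existing online questionnaire in both the pre- and post-intervention waves, and list it as a secondary outcome for Objective 2. A validated measure is preferable, because the Tools section commits to validated instruments. Rename or redescribe the questionnaire so that its label matches its content.

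If the pre-intervention wave has already closed, restate Objective 2 and the label in the confidentiality section in terms of stress and burnout, and say in the analysis section that no conclusion on satisfaction will be drawn from PSS or MBI results.

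The first option costs a little more respondent time on a questionnaire already put at 15 to 20 minutes, and an ethics amendment. The second needs no new data, but gives up the satisfaction part of the objective.

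### The planned pre/post cost contrast omits both the staffing spend and the savings of the 6-month intervention period, so it cannot by itself show whether overall costs fall net of the programme

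*Combined protocol and SAP*

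**What the plan says.** - **What is delivered, and when.** Part 2, Intervention Components, describes Component 2 as better scheduling of ICU nurses. Its one example is a staffing-up "approach where more staff will be scheduled". The number of nurses, the hours and the cost are not given. On timing it says: "There are two specific components that will be implemented concurrently over the 6-month intervention period". The end of Part 2 repeats this: "The two intervention components will be implemented with ICU staff members over the 6-month intervention period".
- **What is compared.** Part 3, Sample Size (Patient Data), states that "the data collected during the intervention period will not be included in the pre-post-intervention analyses". Of the intervention-period data it adds that "it will be used for quality assurance (i.e., stopping rules during interim analysis) and to further contextualize changes using run charts, as needed"; the example it gives is albumin use, not cost.
- **What is measured.** Part 3, Goals of Evaluation: "The primary outcomes of focus are ICU costs and ICU quality metrics". Under Data Collection, ICU costs come from case costing in four lines: total, direct, indirect (overhead tied to patient service) and cost per patient. The direct line reads "ICU direct costs (i.e., all expenses to the hospital with fee codes linked to patient chart". Staff absenteeism is collected. Overtime and scheduled nursing hours are not listed.
- **What is to be concluded.** Objective 1 (end of Part 1) is to lower ICU costs, in part through less overtime. Goals of Evaluation asks whether the overall cost of ICU care falls. Parts 1 and 2 both propose "savings of approximately one million dollars per year for both TOH and the Montfort Hospital".

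**The concern.** If more nurses are rostered, the hospital spends money in the expectation of recovering it through less overtime and absenteeism. Whether the programme saves money depends on the balance of the two. The planned analysis compares the months before delivery with the months after it and measures neither side of that balance directly: no added hours, no overtime. A fall in case cost between the two windows is a gross change. It could coexist with a net saving or a net loss over the year, and the planned data would not tell these apart. What is at stake is the reading of a primary outcome, and any later statement about annual savings.

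**Working it through.** **1. The plan's own figures.** Civic Campus accrual is 120 patients per month: 120 x 3 = 360 before, 120 x 6 = 720 during, 120 x 3 = 360 after; 360 + 720 + 360 = 1,440, as stated. The excluded share is 720 / 1,440 = 50%, and it is the whole of the stated delivery period. The $1 million projection has no derivation in the documents and cannot be reproduced.

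**2. Periods side by side.**

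| Period | Programme delivered? | In the cost contrast? |
|---|---|---|
| Pre, 3 months | No | Yes |
| Intervention, 6 months | Yes | No |
| Post, 3 months | Not stated | Yes |

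**3. What the contrast captures depends on two facts that are not stated.**

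- *Scheduling stops at month 6.* The added hours fall wholly outside both windows. Any overtime relief that depends on the schedule may stop as well.
- *Scheduling continues and case costing includes nursing labour.* The post-period running cost enters the contrast, which then compares usual running with programme running. The 6-month spend is still outside it.
- *Scheduling continues and case costing does not include nursing labour.* Neither the added hours nor the avoided overtime appears in either window.

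In all three cases the spend and the savings of the six delivery months are missing.

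**4. Scale of the gross spend.** Staffing level and wage are assumptions; the documents give neither.

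- Hours for one extra nurse around the clock: 182.5 days x 24 h = 4,380 h per site.
- At $45 per hour: 4,380 x 45 = $197,100. At $60 per hour: 4,380 x 60 = $262,800.
- Two sites with the same increment: $394,200 to $525,600.
- With Montfort's increment scaled to its staff count (50 against 194 at the Civic Campus): multiply the one-site figure by 1 + 50/194 = 1.258, giving about $248,000 to $331,000.

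**5. Set against the projection.** Half a year of $1 million is $500,000 if the figure is for the two hospitals together, or $1,000,000 if it is for each.

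- Equal increments: 394,200 / 500,000 = 79% to 525,600 / 500,000 = 105%; halved, 39% to 53%.
- Scaled increments: 248,000 / 500,000 = 50% to 331,000 / 500,000 = 66%; halved, 25% to 33%.

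These ratios show only that the omitted item could be of the same order as the saving sought. They are gross of avoided overtime, and the documents do not say whether the $1 million is itself gross or net.

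**The case against.** The strongest reply has five parts.

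- **Staffing up is only an example.** Part 1 describes the component as matching nurse numbers to each shift, so there may be little or no net added spend. This stands: the size is unknown.
- **Total or indirect case costs may already include nursing labour.** If the schedule also continues after month 6, post versus pre is a reasonable steady-state comparison. This stands as a possibility, but the documents settle neither point, and the delivery months remain outside the contrast.
- **The workshop may cost nothing extra.** It is held within a regular department meeting. This stands.
- **The $1 million is a projection.** It is worded tentatively, and Data Analysis plans no annual-savings estimate. This also stands, but Goals of Evaluation still asks whether overall costs fall, and the planned contrast does not answer that.
- **Intervention-period costs may be available.** Case costing covers the study period, and the Respondents text speaks of a 6-month study period for assessing effectiveness (which does not fit the 12-month schedule and should be reconciled). Availability helps the remedy; it does not put programme cost into the comparison.

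A reader might also infer that the omission biases the result one way, in favour of the intervention. The documents do not support that. The excluded months hold savings as well as spending, and their balance is not known.

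**Conclusion.** The gap is real, but it lies in what the contrast can show and is not a demonstrated bias. Followed as written, the primary cost analysis gives a gross change in case cost between two 3-month windows. It leaves out the programme's spend and its savings over the six months of delivery, and it has no measure of scheduled hours or overtime from which a net figure could be built. On an assumed one extra nurse around the clock at an assumed $45-60 per hour, the gross spend is about $197,000-$263,000 per site; the net amount and its sign cannot be derived from the documents. It would go too far to say that the added staffing is certainly paid for only in the excluded months, or that a fall would necessarily be reported as a saving. The first depends on when the scheduling ends, and the second is an inference from the stated objective and projection.

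**What to change.** 1. Under Data Collection, ICU costs, add scheduled nursing hours and overtime hours, with their cost, for all three periods at each site, from hospital payroll or scheduling records.
2. State whether the scheduling continues after month 6, and whether case costing includes nursing labour.
3. Beside the pre/post contrast, report net cost per site on one common time base (per month or per patient-day): change in case cost, plus cost of added scheduled hours, less avoided overtime. Leave out of the added terms any labour already in case costing.
4. For the intervention months, set programme cost against case costs from those same months. Six months of spend should not be added to a difference between two 3-month windows.
5. Count workshop time only if it is paid in addition to the regular meeting.
6. Base any annual-savings statement on the net figure, and say whether the projected $1 million is combined or per hospital.

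The cost is one more data extract per site and a modest amount of analysis. The reported saving may turn out less favourable.
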